#### 13.4 Exclusion Criteria

- a) Any failure to meet above criteria;
- b) Pregnant women or women who are contemplating pregnancy.
- c) Prior history of abusing non-prescribed drugs.
- d) A recent (one-year) history of alcohol abuse.
- e) Renal disease, heart disease or uncontrolled hypertension, liver disease or hepatic cirrhosis.
- f) Active major medical or psychiatric illness; a score of less than 25 on the MMSE.
- g) Significant post-traumatic encephalopathy from head trauma sustained at SCI.
- h) Pain is only nociceptive, due to muscle spasm

**Additional Surgical Exclusion Criteria:**

- 1) Coagulopathy
- 2) Thrombocytopenia or platelet dysfunction
- 3) Inability to cooperate
- 4) Any clinically significant abnormality, not expected on the basis of age (age-related), that is seen in magnetic resonance imaging (MRI).
- 5) Peripheral vascular disease.
- 6) Depression, as defined by a Beck Depression Inventory (BDI-1a), score 30 or above.
- 7) Existing implantable cardiac pacemaker, defibrillator or neurostimulator.
- 8) Diathermy treatment during the course of the study (unless limited to brain and cervical spine and using a head send-receive coil
- 9) Adverse reaction to stimulation (such as inability to stimulate at analgesic levels without causing clinical hypertension or hypotension) or allergy or hypersensitivity to any materials of the neurostimulation system
- 10) Comorbid neurological diseases or disorders, including a history of seizures

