	4. Autonomic dysreflexia can be present but is not a necessary requirement. This is defined as a rise of systolic pressure by more than 30 mm Hg during noxious skin stimulation or when the bladder or bowel is full, or apparently spontaneously over a period of minutes.		
	5. Pain (neuropathic) of moderate severity or greater is present, when the patient is taking medication, with a score of at least 4 on a numerical rating scale (range of 0 to 10).		
6. Treatment with at least two of the following drug classes must have failed to give satisfactory pain relief within the last two years: anticonvulsants (e.g., pregabalin, gabapentin); antidepressants (e.g., trazodone, amitriptyline); NSAIDS (e.g., ibuprofen). In addition, at least one of the following must have proved ineffective: exercise-based rehabilitation, massage therapy using a variety of methods, acupuncture using pressure, needles, heat, or electrical stimulation on specific points on the body and psychological interventions such as cognitive therapy.			
7. Participants on medications for other conditions, such as diabetes, will be considered as candidates for this study. The dose will be monitored throughout the trial. (They will be excluded if the drug is being used to treat epilepsy, Parkinson's diseases, or other brain degenerative diseases.)			
8. The subject must be willing to comply with the protocol including all scheduled visits.			
9. Literate at 8th grade level or above.			
10. The subject must provide a letter of clearance for the DBS surgery from their primary physician.			

Main Criteria for Exclusion
	
Major Exclusion Criteria: Admission to study.
		
	Exclusion Criteria	Measure	Rationale
	Unable to give informed consent	Clinical examination	Protection of human subjects
	Prisoner or ward of the state	History	Vulnerable population
	Pregnancy	Urine or serum pregnancy test	Risk to fetus
	Prior history of abusing non-prescribed drugs	History	Vulnerable population
	Recent (one-year) history of alcohol abuse	History	Vulnerable population
	ASIA motor exam unobtainable	ASIA Motor Score	Baseline scoring needed for determination of change in score
	History of cardiac arrhythmia	History and ECG tracing	Higher risks of arrhythmia with DBS
	Renal disease, heart disease or uncontrolled hypertension, liver disease or hepatic cirrhosis	History	Highly variable rates of recovery

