	Active major medical or psychiatric illness (MMSE<25)	History	Vulnerable population
	Significant post-traumatic encephalopathy from head trauma sustained at SCI	History	Vulnerable population
	Languages without local expertise	Family history	Lack of personnel or appropriate outcomes scales
	Pain is only nociceptive, due to muscle spasm	Physical examination	Neuropathic pain is therapeutic target
		
Major Exclusion Criteria: Treatment/Intervention procedure:
 
 
1. Coagulopathy requiring anticoagulation therapy
 
2. Thrombocytopenia or platelet dysfunction
 
3. Peripheral vascular disease
 
4. Comorbid neurological diseases or disorders, including a history of seizures
 
5. Active systemic infection or concurrent immunosuppressive therapy
 
6. Existing implantable cardiac pacemaker, defibrillator or neurostimulator
 
7. Requiring short-wave or microwave diathermy treatment during the course of the study.
 
8. Inability to cooperate
 
9. Any contraindication to MRI studies (All future MRIs, with the exception of brain MRIs, are excluded.)
 
10. Adverse reaction to stimulation (such as inability to stimulate at analgesic levels without causing clinical hypertension or hypotension) or allergy or hypersensitivity to any materials of the neurostimulation system
 
11. Depression, as defined by a Beck Depression Inventory (BDI-1a) score of 30 or above.
 
12. Subjects with any clinically significant abnormality, not expected on the basis of age (age-related), that is seen in magnetic resonance imaging (MRI).
 
	

Approximate Number of Patients
	
A maximum of 12 participants with incomplete or complete SCI and neuropathic pain at or below the level of injury.

Approximate Number of Study Centers
	
Two sites (VA Medical Center & University of Miami - Miller School of Medicine)

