### 13.3 Inclusion Criteria

- a) Age: 22 - 60 years old at last birthday;
- b) Diagnosis of traumatic SCI at or above the 12th thoracic segment (T12) that occurred >365 days;
- c) Neuropathic pain below the level of injury, as determined based on pain in an area with neurological deficit and described as burning, shooting, electric, stinging etc.

- d) The injury must have occurred at least 1 year prior to entering the study and participants must have experienced chronic pain for a minimum of six months.
- e) The disability must have a grade on the American Spinal Injury Association Impairment Scale (AIS) of ASIA-A, ASIA-B, ASIA-C or ASIA-D as determined by qualified examiners.
- f) Pain (neuropathic) of moderate severity or greater is present, when the patient is taking their routine pain medication, with a score of at least 4 on a numerical rating scale (range of 0 to 10).
- g) Participants who are on medications for other conditions, such as diabetes, will be considered as candidates for this study. The dose will be monitored throughout the trial. (They will be excluded if the drug is being used to treat epilepsy, Parkinson's diseases, or other brain degenerative diseases.)
- h) Participants will be allowed to utilize over-the-counter drugs such as NSAIDs, acetaminophen and aspirin. Their use will be documented in the weekly pain assessments. A list of "allowed" medications will be provided to study participants. After the surgery, patients will be allowed to take stay on the protocol if they take Tramadol (50-100 mg, 2 times a day for up to 2 weeks) as a rescue drug in addition to their stable medication.
- i) The patient must be taking pain medication to maintain a stable level of medication from 4 weeks before surgery to 12 weeks after (the primary endpoint), except on the day of surgery. On the day of the surgery, in the presence of a physician who can provide immediate backup pain control if needed, medications will be stopped until the acute effects of DBS on analgesia have been evaluated.
- j) The participant must be willing to comply with the protocol including all scheduled visits.
- k) Autonomic dysreflexia can be present but is not a necessary requirement. Autonomic dysreflexia will be defined as rise of systolic pressure by more than 30 mm Hg during noxious skin stimulation or when the bladder or bowel are full, or apparently spontaneously over a period of minutes
- l) Literate at 8th grade level or above.

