##### B. Prohibited Treatment

Investigational drugs and any other intervention (not part of the guidelines for management of SCI) known to have a potential impact on outcome are prohibited.

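### Section 13.4 attaches a garbled exception to the diathermy exclusion that the synopsis lacks, and Section 13 never names immunosuppressive therapy, which the synopsis excludes

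*Combined protocol and SAP*

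**What the plan says.** The protocol lists exclusions twice: in the synopsis (Section 3) and in Section 13.4.

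- **Diathermy.** Synopsis treatment/intervention item 7 excludes anyone "Requiring short-wave or microwave diathermy treatment during the course of the study", without exception. Section 13.4, Additional Surgical Exclusion Criteria, item 8 reads "Diathermy treatment during the course of the study (unless limited to brain and cervical spine and using a head send-receive coil". The text stops there, inside an open parenthesis.
- **Infection and immunosuppression.** Synopsis treatment item 5 excludes "Active systemic infection or concurrent immunosuppressive therapy". Section 13 has no matching item.
- **Other medication.** Section 13.3(g) says "Participants who are on medications for other conditions, such as diabetes, will be considered as candidates for this study". Its only drug-based bar is "They will be excluded if the drug is being used to treat epilepsy", extended to Parkinson's disease and other degenerative brain disease.
- **MRI and arrhythmia.** Synopsis treatment item 9 excludes "Any contraindication to MRI studies (All future MRIs, with the exception of brain MRIs, are excluded", and the synopsis admission table lists "History of cardiac arrhythmia". Section 13.4 names neither.
- **Prohibited treatment.** Section 14.6B bars investigational drugs and "any other intervention (not part of the guidelines for management of SCI) known to have a potential impact on outcome are prohibited". It mentions neither diathermy nor MRI.

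**The concern.** These are working entry rules for a brain implant, and nothing in the protocol says which list governs when they differ. Someone screening from Section 13 would meet a diathermy rule that the synopsis contradicts. The same person could take a candidate on immunosuppressive treatment forward without seeing that the synopsis excludes them.

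Both matters bear on hazards that the protocol itself describes. Section 9.1 has the leads and extensions running under the skin of the neck and through the skull, which is the region named in the exception. Section 14.4 gives infection as the most common reason for removing the device, with a 1.5% removal risk at the institution. Section 10 lists delayed device infection as a risk.

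The lists also matter after entry. Section 13.5(b) makes newly discovered ineligibility the anticipated ground for the investigator to end participation, and Section 19.4 requires important eligibility deviations to be documented. Neither can be applied consistently to two different lists.

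**Working it through.** There is no plan figure to reproduce. The check is an item-by-item match of the synopsis exclusions against Section 13.4.

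**Count.**

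- Synopsis admission table: 12 rows. Seven match 13.4(b) to (h). Five do not: consent, prisoner or ward, unobtainable ASIA motor exam, arrhythmia, language.
- Synopsis treatment list: 12 items. Ten match surgical items 1 to 10. Two do not: item 5 (infection or immunosuppression) and item 9 (MRI).
- Total 12 + 12 = 24; matched 7 + 10 = 17; unmatched 24 − 17 = 7.
- Three of the seven bear on device or surgical safety: arrhythmia, MRI contraindication, and infection or immunosuppression. The other four are outside this point.
- Item 13.4(a) does not bring the seven back in, because it refers only to the inclusion criteria in 13.3.

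Among the 17 matches, diathermy differs in two ways: 13.4 has a broader base (any diathermy) but adds the exception. Two others are stricter in 13.4: coagulopathy has no anticoagulation qualifier, and women contemplating pregnancy are added.

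**Cover for the three safety items.**

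| Synopsis exclusion | Other cover | What remains |
|---|---|---|
| MRI contraindication | Preoperative brain MRI for every patient (14.3.2); MR check for implanted pumps (10.1) | Nearly closed at entry |
| Arrhythmia | Heart disease, 13.4(e); pacemaker or defibrillator, surgical item 7; week 7 ECG (Table 2) | Partly covered |
| Active infection | Major medical illness, 13.4(f); week 2 viral serology; blood counts at weeks 2 and 8; temperature at weeks 1, 2, 7 and 8; physician's clearance, 13.3(n) | Partly covered |
| Immunosuppressive therapy | Only general judgment under 13.4(f) and 13.3(n) | Not named anywhere in Section 13 |

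The last two rows are one synopsis item, split because the cover differs. The synopsis carries the same other-medications sentence as 13.3(g), but there treatment item 5 limits it. In Section 13 nothing specific does.

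**Reading item 8.** The exception needs two things together: restriction to brain and cervical spine, and use of a head send-receive coil. A coil of that kind belongs to MRI, and the item that 13.4 lacks is the MRI item. Both facts, with the open parenthesis, suggest an MRI condition merged into the diathermy line. If so, a second conflict appears: synopsis item 9 allows later MRI of the brain only, while this text would add the cervical spine. Injuries at or above T12 are eligible under 13.3(b), so cervical cases can enter and cervical imaging is a realistic question.

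**How long the limits run.** Both diathermy items apply during the course of the study. Synopsis item 9 speaks of all future MRIs and sets no end date. Section 12.6.1 describes weeks 53 to 156 as an extension of the study. The existing wording therefore reaches the extension.

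**The case against.** The strongest reply is that item 8 is a damaged line, not a working permission. It breaks off mid-parenthesis, so text may have been lost in drafting or in conversion from PDF. A reader might infer that the protocol authorises diathermy over an implanted head. The documents do not support that: both parts of the exception must hold, and a diathermy session would not meet the coil condition. This part stands, and it lowers confidence about what item 8 was meant to say. It does not remove the contradiction, since one list is unconditional and the other is not.

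A second reply is that the synopsis and Section 13.4 can be applied together, so an omission from one is not a conflict. A careful team might do that, and 13.3(g) only makes people candidates. But the protocol does not instruct it. Section 14.1 sends screeners to Tables 1 and 2, which mention neither diathermy nor immunosuppression. The reply carries most weight for arrhythmia, active infection and MRI contraindication, which have other cover, and least for immunosuppressive therapy.

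A reader might also infer from Section 14.6B that the protocol sets no diathermy or MRI limit after implantation. That does not follow. The limits exist in the eligibility items and run through the extension, and 14.6B is aimed at interventions that could affect outcome. Consent forms are not in the reviewed text, so what participants are told cannot be judged.

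**Conclusion.** The point holds in two parts. First, Section 13.4 item 8 and synopsis item 7 disagree on diathermy, and item 8 is garbled. Second, Section 13 omits the synopsis exclusion for infection or immunosuppression, with immunosuppressive therapy as the real gap. The missing arrhythmia and MRI-contraindication items are lesser inconsistencies, and the silence of 14.6B is not an error.

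Confidence is high that the two lists differ, and medium on the intended meaning of item 8, which rests on the printed text being what the sponsor wrote. The documents give no basis for estimating how many of the 12 participants are affected. The matter is participant safety and consistent eligibility; it does not touch sample size or analysis. It should be fixed.

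**What to change.** 1. Check item 8 against the source file. Then make the diathermy exclusion unconditional and identical in synopsis item 7 and 13.4 item 8. The broader base in 13.4, any diathermy during the study, would serve both.
2. Do not simply discard the region-and-coil text, which holds the protocol's only mention of a head send-receive coil. If it was meant as an MRI condition, move it to synopsis item 9 and a matching 13.4 item once device experts confirm it, and settle whether the permitted region is brain only or brain and cervical spine.
3. Add to 13.4 the synopsis wording "Active systemic infection or concurrent immunosuppressive therapy". For consistency, add the arrhythmia and MRI-contraindication items too.
4. Update any screening form the sites use. Repeating the diathermy and MRI limits in 14.6B is an optional convenience.

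The cost is a wording amendment, with slightly narrower eligibility for anyone who screens from 13.4 alone. Sample size and analysis do not change.

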**13.5 Withdrawal Criteria:**

- a) Participants may withdraw consent to participate in this study at any time by informing the Principal Investigator. No further procedures will be performed or information will be collected from participants that withdraw consent. Previously collected data and samples will be used for the study analysis;
- b) The only anticipated circumstance under which the Principal Investigator would terminate a subject's participation is if information was obtained which made the subject ineligible for the study. The primary reason for this premature termination is to be indicated by selecting one of the following definitions:
  - Gradual deterioration in neurological status from incomplete to complete SCI, or change in ASIA grade to a more severe level: B to A, C to A or B, D to A or B or C;
  - Unresolved post-surgical wound infection;
  - Onset of confounding neurological problems such as severe dysesthesia, severe neuropathic pain or changing neurological level;
  - Serious adverse event: discontinuation due to a serious adverse event;
  - Lost to follow-up: the subject fails to return to the study site for scheduled visits and does not respond to attempts to contact;
  - Withdrew consent: the subject decides to stop his participation for any other reason than an adverse event, or is unable to complete the study as described in the study protocol;
  - Administrative: the Sponsor decides to terminate an individual subject or decides to discontinue the study due to general safety concerns;
  - Protocol violation: anything that is a direct and significant violation of the clinical study protocol.

## 14 TREATMENT OF PARTICIPANTS

### 14.1 Recruitment and Screening Procedures and Assessments:

Screening and recruitment of participants will take place at the Veterans Hospital and at The Miami Project to Cure Paralysis. Participants will be inpatients or outpatients at Veterans Hospital or University of Miami Hospital (UMH). After admission, the PI or designated representative will be informed of the patient and their history will be carefully screened for relevant selection criteria (as outlined in Table 1, and Table 2 in section 13.6) and the patient's MRI of the spine will be reviewed. Patients with spinal cord transection and contusive signal change exceeding 3 cm in length will not be eligible for the study. Eligible patients will be informed of the study, counseled regarding its key steps, and procedures, and asked to provide Informed Consent.

### 14.2 Method of Assigning Participants to Treatment Groups:

Not applicable. This study will employ an open label, non-randomized, and non-placebo controlled design. There will be only one treatment group.

### 14.3 Participant Procedures and Assessments

#### 14.3.1 Baseline Assessments

Participants who remain eligible after all the screening procedures are complete will undergo the following baseline assessments at 2- week, prior to surgical procedures.

- Functional Pain Assessments
  - ISCI basic pain dataset and Neuropathic Pain Symptom Inventory (NPSI)
  - West Haven-Yale Multidimensional Pain Inventory for persons with SCI (MPI-SCI)
  - Allodynia testing
  - Quantitative sensory testing (QST)
- Quality of Life assessments
  - Beck Depression Inventory (BDI, version 1a)
- Autonomic Assessment:
  - Autonomic Standards Assessment (BP, HR, sympathetic skin response)
  - Tilt table exam response.

#### 14.3.2 Surgical Procedures and Assessments.

The surgical procedure for implantation of a PAG/PVG deep brain stimulator is described here. The procedure technique is no different than FDA approved deep brain stimulator procedures for movement disorder. All patients undergo MRI imaging of the brain prior to surgery. Particular imaging sequences consist of thin cut (1-2mm) T1 and T2 weighted images. On the morning of surgery, in the pre-anesthesia holding area, a Cosbid, Robert, Wells (CRW) frame is rigidly affixed to the skull with four point fixation. This is done with local anesthetic injections consisting of .5% Marcaine with epinephrine 1:200,000, a total of 20-30cc is usually used.

Once the frame is in place, the patient will undergo a CT scan of the brain without contrast agent. This CT scan has the localizer rods in place, which create a stereotactic field for precise localization of target. The imaging studies including the CT scan and the prior obtained MRI are uploaded into a Medtronic planning station which allows for manipulation of the images and targeting of the periaqueductal gray. The computer

then outputs an X, Y, and Z coordinate for the chosen target. More than one MRI scan may be necessary if determined by the neurosurgeon, in order to obtain optimal image resolution and fusing with the CT scan by the planning station software.

The patient is then placed on the operating room table in the supine position with the head elevated approximately 45°. The patient's head is fixed in this position with the use of the frame. The entire head is then shaved and the right frontal area of the scalp approximately 11cm back from the nasion and 3.5cm off the midline on the right side is injected with approximately 20cc of 0.5% Marcaine with 1:200,000 epinephrine. The CRW arc with the X,Y, and Z coordinate for the target is then applied to the CRW frame. A small curvilinear incision is then made and a 14mm burr hole is made using a Midas Rex drill. A burr hole cap is applied to the circumference of the burr hole. The dura is then opened using electrocautery exposing the underlying cortical surface. An 11-blade scalpel is then used to score the pia. At this point, a Ben-Gunn Stage is applied to the CRW arc and a cannula is inserted down the center channel of the Ben-Gunn through the burr hole, traversing the right frontal lobe to end at a depth of 25mm above the desired target.

With the use of neurophysiologic monitoring the target is optimized for lead placement. Neurophysiologic monitoring for this target, the periaqueductal grey, is not well defined. Therefore, targeting will be primarily based on image guidance. The lead (model # 3387) itself is then inserted to a pre-defined depth of 237mm. This will place the tip at the chosen target.

Test stimulation will be performed to determine the adequacy of targeting. The patient will report feelings evoked by various stimulation parameters to be sure that appropriate stimulatory effects are felt and that no adverse stimulatory effects are induced at normal programming thresholds (see 14.7).

After confirmation of target accuracy the lead is secured in place. A lead protector is placed over the distal end of the lead which is tunneled into a subgaleal pocket over the right parietal boss. The frontal scalp incision is closed with a combination of 2-0 vicryl and staples. The CRW frame is then removed from the patient's head. An additional CT scan may be performed after the lead implantation procedure to confirm target and ensure no trauma has occurred.

General anesthesia is induced, and the patient is endotracheally intubated. The operating room table is turned 90° and the patient's head turned 70° to the left, placed on a donut head holder with a roll under the shoulder blades to put the neck in slight extension.

The surgical sites are then prepped and draped sterilely. Local anesthetic is injected using 0.5% Marcaine with 1:200,000 epinephrine. A three finger-breadth linear incision is made two finger-breadths below the right clavicle and a subcutaneous pocket is made just over the pectoralis fascia. A counter-incision is made over the distal lead at the parietal boss and the lead is exposed at the parietal boss. The distal lead protector is removed. A subcutaneous passer is used to make a subcutaneous tract from the parietal boss counter-incision to the subclavicular incision. An extension cable is tunneled down the passer and brought out of the subclavicular incision. The passer is then withdrawn and the proximal portion of the extension is connected to the distal portion of the lead. The distal portion of the extension is connected to the superficial channel of the neurostimulator. The neurostimulator and excess extension cable are then inserted into the chest wall pocket and anchored to the pectoralis fascia using a 3-0 prolene stitch. In subjects with implantable programmable pumps, the neurostimulator must be placed at least 8 inches from the implanted pump. The chest incision is re-approximated using 3-0 vicryl stitch in an interrupted, inverted subcuticular manner. Steri-strips are applied to the skin. The parietal boss incision is re-approximated by using 2-0 vicryl for the galea and staples for the skin.

